3.2 Allocation to Treatment Groups

This is a three-arm cluster randomized experiment in which all 147 public healthcare facilities located in Kisumu county will be randomly assigned to one of three study arms: 1. The Community Score Card treatment arm, 2. The Citizen Report Card treatment arm, and 3. The control arm. Each study arm will contain approximately 43 facilities, which, on average, serve approximately 2,500 households each. Prior to randomization, we will ensure the three arms each contain similar numbers of each type of facility by first stratifying by facility type, a designation that includes three categories: 1. clinics and dispensaries (the smallest public facility type); 2. health centers; and 3. hospitals (sub-county or county hospitals).

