3.3 Study Duration, Enrollment and Number of Subjects

Mystery clients and unannounced visitors: All 147 public-sector healthcare facilities in Kisumu County will be included in this study. Each facility will receive two unannounced visitors and three mystery client visits at baseline and then again at endline.

Provider interviews: Provider interviews will be conducted in all 147 public facilities in Kisumu County at baseline and endline. The total number of provider interviews conducted per facility will depend on the facility size but will average three per facility and will range from one to ten. The unannounced visitor will take a roster of providers who offer family planning services that are scheduled to work that day. If the facility has more than ten providers who provide family planning services scheduled to work that day, then ten providers will be randomly selected to participated. If the facility has less than ten providers scheduled to work that day, then all providers who offer family planning services will be interviewed.

Individual-Level Interviews: 18 women will be sampled from each of the 42 clusters in each of the three arms. Households will be selected at random and approached by trained enumerators who will discuss the study and survey with the household head and then approach eligible women to review the consent process. This cross-sectional survey will be conducted at both baseline and endline.

In-depth interviews: Thirty qualitative in-depth interviews will be conducted at endline with providers and community members to explore nuanced perspectives on formal feedback mechanisms and impact on provider job fulfillment. The UNC-based and local research teams will use convenience sampling to ensure that community members and providers who participated in the interventions are included. Once potential respondents have been identified, the local partner will invite potential respondents to participate in the interviews.

Focus Group Discussions: Four focus group discussions will be conducted at endline with two groups per intervention arm. These discussions will bring together key facilitators who were instrumental in the implementation of the two interventions. The UNC-based team will work with our local partner to identify key figures in the implementation process and invite them to join these discussions. Approximately 55 individuals will be recruited to participate in these focus group discussions.

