6 STATISTICAL CONSIDERATION

1.1 Primary Endpoint

Aim 1 Methods: Estimate the Impact of Two Social Accountability Interventions on Modern Contraceptive Use.

Overview. Weak accountability mechanisms in public-sector facilities result in poor provider performance, creating barriers to family planning use among women with a desire to space or limit future pregnancy. The *objective* of this aim is to estimate the impact of the Community Score Card and the Citizen Report Card, relative to the control arm, on current use of a modern contraceptive method. To attain this objective, we will test the *working hypothesis* that social accountability efforts result in increased community empowerment, provider performance, and service utilization which, in turn, increases contraceptive use. Our *approach* to testing the working hypothesis will be to use a difference-in-difference (DiD) model to estimate differential change over time in each of the two treatment areas versus the control area. The *rationale* for this aim is that the results will contribute to a nascent body of literature on the impact of social accountability efforts to increased contraceptive use. Such findings are important because they inform much needed knowledge of effective strategies for reducing unmet need for women living in LICs.

Research Design. To assess the causal effect of the interventions, we will use a difference-indifference (DiD) model to estimate differential change over time in each of the two treatment areas versus the control area. The DiD model is commonly used in the social sciences [45, 46] and is described as follows:

Y=60 + 61POST + 62T1 + 63(POST*T1) + 64T2 + 65(POST*T2) + 64X + ui (1)

In this equation, Y is a binary variable for current modern contraceptive use (0=non-use; 1=use), attained by asking participants, "Are you (or your partner) currently doing something or using any method to delay or avoid getting pregnant?" We will define modern contraceptive methods to include female or male sterilization, intrauterine device, implant, injectable contraception, oral contraceptive pill, or male or female condom.

Stacking pre- and post-data, POST is an indicator variable (0=baseline;1=endline) and T1 and T2 are indicator variables for assignment to the Community Score Card or Citizen Report Card, respectively (1), or control (0). Intervention protocol template_Draft_29AUG2016

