The interaction between POST and T1 or T2 gives the difference between the change in the value of Y in either treatment group versus the same change in the control group. Equation (1) also includes a vector, X, of demographic characteristics. For any covariates that are not balanced across the study arms we will control for them in the regression, using their baseline values [47]. These covariates could include age, religion, ethnicity (tribal group), marital status, literacy/education, parity, distance to public facility, and household wealth. This model can also be used to test whether there is a large difference between the treatments by testing the equality of β 3 and β 5.

Expected Outcomes. This aim is expected to provide critical knowledge of whether social accountability efforts can increase family planning use in LICs. Additionally, this aim will determine whether the two primary approaches to community engagement are largely different in their impact on women's contraceptive behavior. This work is crucial to global efforts to address facility-level barriers to contraceptive use.

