6.1 Sample Size and Power

For the *individual*-level surveys, we estimate a design effect of 1.56 for modern contraceptive prevalence due to our cluster-based sampling procedure, based on information provided in the 2014 Kenya Demographic and Health Survey (KDHS) Final Report, Appendix B, Table B2. We calculate our necessary sample size assuming 1.) 50% current modern contraceptive prevalence in Kisumu; 2.) 42 clusters in each study arm [clusters=facility catchment areas (All public facilities have a catchment area which is clearly defined, mutually exclusive, and exhaustive); we are allowing for potential closure of one facility per arm)]; 3.) an effect size of two standard deviations (which correlates to a change in the prevalence of modern contraceptive use of approximately 10 percentage points). With these parameters, we will need to survey 18 women in each of the 42 clusters in each of the three study arms, resulting in a total sample size of 2,268 women of reproductive age in the individual-level surveys. The 18 women sampled from each cluster will be selected at random. We will follow KDHS procedures in cases where there is more than one eligible woman in the household.

For the *facility*-level surveys we will measure family planning service quality and negative provider behaviors via interviews with one to ten providers, depending on total staff at each of the 147 facilities. This will result in approximately 385 provider interviews, with approximately 128 in each study arm. Unannounced visitors and mystery clients will also be deployed to secure less biased estimates of provider absenteeism, informal fee solicitation, and disrespectful/biased treatment of clients; mystery clients will also collect data on traditional measures of family planning service quality such as choice of methods and information on side effects. All 147 facilities in Kisumu will receive two unannounced visits and three mystery client visits.

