Post-treatment, we will repeat the individual-level survey, within a newly sampled cross-section of the population. We will also repeat all facility-level data collection in all 147 public facilities in the county. The changes in contraceptive use, quality of care, and community engagement resulting from the Community Score Card and the Citizen Report Card interventions will be evaluated via data collected in these pre- and post-intervention surveys. The sampling frame for both individual-level surveys will come from the Kenyan National Bureau of Statistics, which completed a new household-level census in all counties in Kenya in August 2019.

7 STUDY INTERVENTION (drug, device or other intervention details)

- Description

The Community Score Card Approach

In the Community Score Card approach, community members come together to document challenges they encounter when seeking services and develop a corresponding set of indicators that can be used to produce a validated facility score. The score is shared with the community and a collaborative process between key community members and facility staff takes place to develop feasible solutions

and a strategic action plan.

Step 1: Preparation (3 months). During this phase, the PI will consult with the Kisumu County Health Director to confirm the geographic coverage of the community score card intervention (the catchment area of the 43 public healthcare facilities in this arm). Training manuals and facilitation guides will be developed. Experienced facilitators will be identified and trained in the community score-card approach. The communities and facility staff will be engaged and sensitized to the community score card via a meeting that discusses the community score card purpose and approach; a date, location, and general process for conducting the community score cards will be selected/designed.

Step 2: Conducting the community score card with target communities (1 month). During this phase, all communities associated with the targeted facilities will assess the primary barriers to quality family planning service delivery and develop corresponding indicators, assisted by an experienced facilitator. The communities will then each complete the score card and generate ideas for quality improvement.

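### The difference-in-difference model for Aim 1 is unbiased but less precise than an endline comparison adjusted for baseline cluster prevalence: about 60-80% against 88-92% power on the plan's design effect

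*Combined protocol and SAP*

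**What the plan says.** Section 3.2 (Allocation to Treatment Groups) states that the facilities "will be randomly assigned to one of three study arms", after stratification by facility type. Section 6 (1.1 Primary Endpoint, Aim 1 Methods) names the analysis: "we will use a difference-indifference (DiD) model to estimate differential change over time in each of the two treatment areas versus the control area". Equation (1) stacks the two waves and contains POST, main effects for each treatment arm (T1, T2) and their interactions with POST. The interaction is the treatment effect; it "gives the difference between the change in the value of Y in either treatment group versus the same change in the control group".

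On adjustment, the same section says "For any covariates that are not balanced across the study arms we will control for them in the regression". The candidates it lists are demographic and access variables. A cluster's baseline prevalence of modern use is not among them.

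On data, section 3.3 samples 18 women in each of 42 clusters per arm and adds: "This cross-sectional survey will be conducted at both baseline and endline". Section 6.1 confirms that after treatment "we will repeat the individual-level survey, within a newly sampled cross-section of the population". For sample size, section 6.1 says "we estimate a design effect of 1.56 for modern contraceptive prevalence due to our cluster-based sampling procedure" and assumes "50% current modern contraceptive prevalence in Kisumu" with a change of about 10 percentage points. It states no significance level, power or between-wave correlation. It also does not say whether the calculation is for a single-time comparison or for a difference of changes.

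**The concern.** Under randomisation, arm differences at baseline are chance. Giving each arm its own baseline level and subtracting the whole baseline difference adds the sampling error of the baseline survey to that of the endline survey. This pays off only if a cluster's baseline prevalence predicts its endline prevalence well. Here different women are interviewed in each wave, only 18 per cluster, so the link between waves runs through the cluster alone and is weak.

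At stake is the precision of the two primary estimates, the POST-by-arm coefficients. A true 10-point effect could be missed because of the estimator, although the data already planned support a more precise one.

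**Working it through.** **Plan's own figure.** 18 × 42 × 3 = 2,268 women per survey, or 756 per arm, as stated. The 18 per cluster cannot be derived uniquely, because significance level and power are not given. Three candidates for 50% against 60%:
- Single-time two-proportion comparison, two-sided 5%, 80% power: 388 × 1.56 = 605 per arm.
- The same at two-sided 2.5%: 470 × 1.56 = 733 per arm; 733/42 = 17.5, rounded up to 18 per cluster.
- Difference of changes, two-sided 5%, 80% power, fully persistent cluster effects: (1.96 + 0.842)² × 4 × 0.25 × (1 − 0.033)/0.10² = 759 per arm.

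**Inputs from the plan.** 42 clusters of 18 women per arm per wave; prevalence 50%; design effect 1.56; effect 10 points; independent cross-sections in the same clusters.

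**Assumptions.** Two-sided 5% per comparison; 1.56 applies at 18 women per cluster; binomial variance 0.25 throughout; no gain from covariates or stratification. The persistence of cluster effects between waves is not stated, so its full range of 0 to 1 is shown.

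**Step 1. Intracluster correlation.** (1.56 − 1)/(18 − 1) = 0.033.

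**Step 2. Correlation of a cluster's two observed prevalences.** R = persistence × 18 × 0.033/1.56, which is at most 0.38.

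**Step 3. Variances.** One arm in one wave: v = 0.25 × 1.56/756 = 0.000516.
- Endline only: 2v
- Difference-in-difference: 4v(1 − R)
- Endline adjusted for baseline cluster prevalence: 2v(1 − R²)

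The ratio of the second to the third is 4v(1 − R)/[2v(1 − R²)] = 2/(1 + R), which exceeds 1 for every R below 1. The ratio of the second to the first is 2(1 − R), which falls below 1 only if R exceeds 0.5.

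**Step 4. Power** = Φ(0.10/SE − 1.96). Endline only: SE = √0.001032 = 3.2 points, power 88%.

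| Persistence | R | DiD SE (points) | DiD power | Adjusted SE (points) | Adjusted power | Variance ratio 2/(1+R) |
|---|---|---|---|---|---|---|
| 0 | 0 | 4.5 | 60% | 3.2 | 88% | 2.00 |
| 0.5 | 0.19 | 4.1 | 69% | 3.2 | 89% | 1.68 |
| 0.8 | 0.30 | 3.8 | 75% | 3.1 | 90% | 1.53 |
| 1 | 0.38 | 3.6 | 80% | 3.0 | 92% | 1.45 |

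A simulation of binary outcomes in 42 clusters per arm (8,000 runs per setting, tests on cluster means) gave 59%, 68%, 74% and 79% for the difference-in-difference. The adjusted analysis gave 88%, 88%, 89% and 91%.

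**Step 5. Sensitivity.**
- At two-sided 2.5% (critical value 2.24), the same standard errors give 48% to 71% for the difference-in-difference and 81% to 87% adjusted.
- With all 147/3 = 49 clusters per arm, v = 0.25 × 1.56/882 = 0.000442. Standard errors are 4.2 to 3.3 points (power 66% to 86%) against 3.0 to 2.8 points (92% to 95%).
- For design effect D at 18 women, the largest R is 18(D − 1)/(17D). It passes 0.5 when D exceeds 18/9.5, about 1.9.

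**The case against.** Five points can be made in favour of the plan.

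- **The plan may have been sized for this model.** The 759 women per arm found above is close to the planned 756. That could explain the number and would mean about 80% power. But it is the best case, requiring fully persistent cluster effects, and a single-time comparison at two-sided 2.5% fits as well. Sizing for an estimator does not make it the more precise one.
- **The 60% end is extreme.** It requires a catchment area's level in 2021 to say nothing about its level in 2022/23. This is fair: the documents give no between-wave correlation, so 60% and 80% are the ends of a range.
- **The design effect is borrowed from a national survey, and the documents do not give that survey's take per cluster.** If it were 10 (an assumption), the intracluster correlation would be 0.56/9 = 0.062, the design effect at 18 women 2.06 and the largest R 0.54. With stable clusters, the difference-in-difference would then have 81% power against 77% for endline only, but still less than the 90% with adjustment. So a reader who infers that the planned model is always worse than ignoring the baseline goes beyond the documents.
- **Covariates and stratification are left out of the calculation.** This is true. Either estimator can use them, and the ratio 2/(1+R) then applies with R taken after that adjustment.
- **Differencing removes persistent recruitment differences between arms.** The documents do not say that baseline recruitment precedes, or is blind to, allocation. Adjustment removes such differences only in part, which is a reason to keep equation (1) as a sensitivity analysis.

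A reader might also infer that the baseline survey is wasted. It is not: equation (1) uses it, and it supports the balance check and the Aim 2 measures.

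**Conclusion.** The point holds as one of efficiency, not validity. Equation (1) is unbiased under randomisation. It is less precise than the baseline-adjusted endline analysis by the factor 2/(1+R), and that ranking does not depend on the design effect, the significance level or the stability of clusters.

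The sizes do depend on assumptions. With 1.56 applying at 18 women per cluster, two-sided 5% and a 10-point effect from 50%, a true effect would be missed in roughly 20% to 40% of trials under equation (1), against 8% to 12% with adjustment. Baseline adjustment adds only 0 to 4 percentage points of power to the 88% of endline only, so most of the gain comes from not differencing. Under the same assumption the planned model is also less precise than endline only. That could reverse if the true design effect exceeded about 1.9 and cluster effects were very stable.

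These figures should not be carried over to Aim 2. The documents give a design effect only for modern contraceptive prevalence, and facility measures repeated at the same facilities may correlate more strongly between waves.

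**What to change.** In section 6 (1.1 Primary Endpoint), and wherever the difference-in-difference is named as the Aim 1 analysis, make the primary model an endline linear (risk-difference) regression. Regress modern use on T1, T2, facility-type stratum and the cluster's baseline modern-use prevalence, with cluster-robust variance. The linear form keeps the effect on the percentage-point scale used in section 6.1. The comparison of the two interventions becomes a test that the T1 and T2 coefficients are equal. Keep equation (1) as a named sensitivity analysis. State the significance level, the target power and the assumed between-wave correlation in section 6.1, so that the sample size can be checked against the chosen model.

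The same form may be used for Aim 2 outcomes measured in both waves, without claiming a particular gain.

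The cost is analysis wording only, with no new data. The small downside is greater reliance on the randomisation and on recruitment not differing by arm, which the retained sensitivity analysis helps to check.

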Overview. The changes that take place between intervention activities and the primary health outcome are referred to as *linking constructs* and are important in the evaluation of social accountability interventions. The *objective* of this aim is to estimate the impact of the two treatments, relative to the control arm, on several outcomes that potentially occur along the causal pathway from the treatments to the primary outcome of increased contraceptive use. To attain this objective, we will test the *working hypothesis* that social accountability efforts result in increased community empowerment and quality of care. Our *approach* to testing this working hypothesis will be to, once again, use a DiD model to estimate differential change over time in each of the two treatment areas versus the control area. Our *rationale* for this aim is that, currently, little is known about the causal mechanisms through which community monitoring activities impact health behaviors. *We expect* to identify the primary intermediate outcomes between the intervention and outcome. Such findings are important because they provide valuable information on which specific components of the interventions produce the change in contraceptive behavior.

Research Design. As in Aim #1, we will use DiD models to estimate differential change in each of the

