1.1 Statistical Methods

Intervention protocol template_Draft_29AUG2016

Our approach to testing the working hypothesis will be to use a difference-in-difference (DiD) model to estimate differential change over time in each of the two treatment areas versus the control area. The rationale for this aim is that the results will contribute to a nascent body of literature on the impact of social accountability interventions on family planning use. We expect to identify the potential contribution of social accountability efforts to increased contraceptive use. Such findings are important because they inform much needed knowledge of effective strategies for reducing unmet need for women living in LICs.

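### The primary difference-in-difference model has no facility-level inference: fitted with independent errors, an assumed two-sided 5% test has a true type I error of about 4.6% to 11.7%

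*Combined protocol and SAP*

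**What the plan says.** Section 3.2 makes the facility the unit of randomisation: "all 147 public healthcare facilities located in Kisumu county will be randomly assigned to one of three study arms". Section 3.3 sets the survey size: "18 women will be sampled from each of the 42 clusters in each of the three arms". Endline uses new women from the same catchments: "we will repeat the individual-level survey, within a newly sampled cross-section of the population" (Section 6.1).

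Section 6.1 expects clustering in the primary outcome: "we estimate a design effect of 1.56 for modern contraceptive prevalence due to our cluster-based sampling procedure".

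The primary analysis is in Section 6, under 1.1 Primary Endpoint: "Y=60 + 61POST + 62T1 + 63(POST*T1) + 64T2 + 65(POST*T2) + 64X + ui (1". The digit 6 in front of each subscript is a misread beta. The two effects of interest are β3 (Community Score Card) and β5 (Citizen Report Card), and a test of β3 = β5 is also offered. On covariates, the section says "Equation (1) also includes a vector, X, of demographic characteristics"; the examples listed contain no facility identifier.

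The section headed 1.1 Statistical Methods adds only that the investigators will "use a difference-in-difference (DiD) model to estimate differential change over time in each of the two treatment areas versus the control area". Aim 2 inherits the approach: "As in Aim #1, we will use DiD models to estimate differential change in each of the" two treatment areas against control.

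**The concern.** In a cluster-randomised trial the test must respect the randomised unit. Here clustering enters the sample size but not the analysis. No part of the analysis text mentions a random or fixed facility effect, a facility-by-wave effect, GEE, cluster-robust standard errors, cluster-level summaries or a permutation test. The one alternative analysis described, the contamination-adjusted intention-to-treat analysis, does not deal with clustering.

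An analyst who fits equation (1) with ordinary standard errors would be following the plan. Intervals and p-values for β3, β5 and β3 = β5 would then generally be too optimistic. An analyst who clusters would be following the plan too. The primary test therefore depends on an unstated choice that could be made after the data are seen.

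**Working it through.** **Inputs from the documents.** m = 18 women per cluster per wave and 42 clusters per arm (Sections 3.3 and 6.1); design effect 1.56 and prevalence 50% (Section 6.1); a new cross-section at endline (Section 6.1).

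**Assumptions.** A two-sided 5% test (no alpha, sidedness or power is stated); 1.56 applies at 18 women per cluster; no covariates. The between-wave correlation of catchment effects, here CAC, is not given, so it is varied from 0 to 1.

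**The plan's own figure.** 18 × 42 × 3 = 2,268 women per wave, as stated. The choice of 18 per cluster cannot be checked, because alpha and power are missing.

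**Intracluster correlation.** ρ = (1.56 − 1)/(18 − 1) = 0.56/17 = 0.0329.

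**Variance of the interaction.** With n = 18 × 42 = 756 women per arm and wave, independent errors give a variance of 4 × 0.25/756, so SE = 0.0364 and the 95% half-width is 1.96 × 0.0364 = 7.1 percentage points. With catchment effects present in both waves, this variance is multiplied by

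R = 1 + (m − 1)ρ − mρ × CAC = 1.56 − 18 × 0.0329 × CAC.

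R does not depend on the number of clusters, so the differing facility counts per arm in the document do not affect it.

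**Type I error of the independent-errors test.** 2 × [1 − Φ(1.96/√R)].

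| CAC | R | Type I error | Coverage of a nominal 95% interval | Correct half-width (points) |
|---|---|---|---|---|
| 0 | 1.560 | 11.7% | 88.3% | 8.9 |
| 0.5 | 1.264 | 8.1% | 91.9% | 8.0 |
| 0.8 | 1.086 | 6.0% | 94.0% | 7.4 |
| 1 | 0.967 | 4.6% | 95.4% | 7.0 |

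R = 1 when CAC = 17/18 = 0.944. At CAC = 0 the independent-errors SE is 1/√1.56 = 0.80 of the correct one, that is, 20% too small; the correct SE is 25% larger.

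**Simulation.** Binary outcome, 42 clusters of 18 women per arm and wave, 40,000 replicates, Monte Carlo SE about 0.15 points at a 10% rate. Independent errors rejected β3 = 0 in 11.9%, 8.3%, 6.3% and 4.9% of replicates at CAC 0, 0.5, 0.8 and 1, and β3 = β5 in 12.2%, 8.6%, 6.2% and 4.7%. Clustering on facility across waves (t with 82 degrees of freedom) gave 5.0–5.1% and 4.9–5.2%.

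**Sensitivity to the cluster size behind 1.56.** Section 6.1 takes 1.56 from a national survey and does not give that survey's cluster size. If 1.56 applies at 10, 15, 25 or 30 women per cluster:

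| Women per cluster behind 1.56 | Type I error, CAC 0 | Type I error, CAC 0.8 |
|---|---|---|
| 10 | 17.2% | 6.9% |
| 15 | 13.1% | 6.2% |
| 25 | 9.7% | 5.7% |
| 30 | 8.9% | 5.6% |

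At CAC 1 the range is 4.3–4.8%. In the 10-woman case ρ = 0.56/9 = 0.062 and the design effect at 18 women is 1 + 17 × 0.062 = 2.06, so the correct interval at CAC 0 is √2.06 − 1, about 43%, wider than the independent-errors one.

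**Aim 2.** No design effect or intracluster correlation is given for its outcomes, so no figure can be computed.

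**The case against.** The strongest reply is that the plan is silent, not wrong. Equation (1) gives a mean structure, no sentence says the errors are independent, and the document treats the trial as clustered throughout, so a competent analyst would cluster. It is true that the error rates describe one permissible fit and not a stated intention. But this document is the analysis plan, it refers to no other, and its Statistical Methods section should fix the primary test. The case rests on the absence of any clustering text, not on the subscript of a badly extracted error term.

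The size is also open to challenge. The 11.7% needs catchment effects that are unrelated between waves. The same catchments are surveyed in 2021 and 2022/23, and at a correlation of 0.8 the error is only 6.0%. Covariates such as distance, ethnicity and wealth, and allocation stratified by facility type, could absorb some between-catchment variance. These points stand as limits on the figure: it is approximate and unadjusted, and inflation is likely but not certain. They do not remove the gap, because without facility-level inference the test is valid only if catchment effects are almost perfectly stable or largely explained by covariates, and the plan assumes neither.

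**Conclusion.** The concern holds and must be fixed. The plan allows for clustering when choosing the sample size and does not carry it into the primary analysis. If equation (1) is fitted with independent errors, the type I error per comparison is about 4.6% to 11.7% instead of 5%, and nominal 95% intervals cover 95.4% down to 88.3%. The inflation occurs when the between-wave correlation of catchment effects is below about 0.94.

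The range rests on the three assumptions listed in the working. The upper end would be higher if 1.56 came from clusters smaller than 18 women, and lower if from larger ones. The missing specification itself is certain from the text. For Aim 2 the same specification is missing, but neither the direction nor the size of any error can be determined.

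**What to change.** Keep equation (1) as the mean model and add one sentence: inference for β3, β5, the test of β3 = β5 and every Aim 2 difference-in-difference model uses standard errors clustered on the randomised facility across both waves, with t degrees of freedom based on the number of facilities. A mixed model with random facility and facility-by-wave effects is a sound alternative. Name one of the two as primary before the outcome data are analysed.

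The cost is the sentence and one software option, with no new data. With 1.56 applied at 18 women, intervals become up to 25% wider if catchment effects are uncorrelated between waves (8.9 against 7.1 points) and hardly change if they are stable. If 1.56 came from smaller clusters, the widening could be greater. Where intervals do widen, the wider ones are the correct ones.

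### Facility type defines the randomisation strata but is missing from the DiD model; with facility-clustered standard errors, leaving out facility type x POST costs a little power if change differs by type

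*Combined protocol and SAP*

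**What the plan says.** Section 3.2 (Allocation to Treatment Groups), like section 3.1 and the synopsis, stratifies the randomisation: "we will ensure the three arms each contain similar numbers of each type of facility by first stratifying by facility type". The three types are clinics and dispensaries, health centers, and hospitals. The documents do not give the number of facilities of each type.

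The primary model is in section 6, 1.1 Primary Endpoint (the betas appear as 6 in the extracted text): "Y=60 + 61POST + 62T1 + 63(POST*T1) + 64T2 + 65(POST*T2) + 64X + ui (1". Of X the plan says "Equation (1) also includes a vector, X, of demographic characteristics". The entry rule is "For any covariates that are not balanced across the study arms we will control for them in the regression", and the candidates are listed as "These covariates could include age, religion, ethnicity (tribal group), marital status, literacy/education, parity, distance to public facility, and household wealth". That list is open, but it names only characteristics of women and households, and distance to the facility. Aim 2 applies DiD models in the same way. The short Statistical Methods section adds nothing on strata.

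No method for clustered SEs is given. The equation carries only the individual error term, and clustering enters the calculations only as the sample-size design effect in section 6.1.

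**The concern.** Stratified allocation removes between-stratum variation from the comparison of arms. A facility-level analysis that leaves the strata out still counts that variation as residual noise, so the SE it reports is larger than the real sampling error of the estimate. The test is then conservative, and part of the precision bought by stratifying is not used.

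In a DiD this applies only to differences in change. A constant gap between, say, hospital and dispensary catchments cancels, because the same catchments contribute 18 women at each wave. What matters is whether contraceptive use moves at different rates by facility type. The plan's covariate rule looks for imbalance between arms, and stratification is there to prevent that imbalance, so the rule is unlikely to bring facility type in.

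**Working it through.** **Inputs from the documents.** Section 6.1 gives 42 clusters per arm, 18 women per cluster, an effect of about 10 points, "50% current modern contraceptive prevalence in Kisumu" and "we estimate a design effect of 1.56 for modern contraceptive prevalence". The stated total reproduces: 18 x 42 x 3 = 2,268 women per wave, or 756 per arm. The 18 per cluster cannot be uniquely re-derived, because alpha and power are not stated. I use 42 clusters because section 6.1 does, although 147/3 = 49.

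**Inputs assumed.** Two-sided 5%; correlation r between a cluster's baseline and endline levels; type shares from 80/15/5% to 60/30/10% (clinics and dispensaries / health centers / hospitals); differences in change by type.

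**Step 1: ICC.** (1.56 - 1)/(18 - 1) = 0.56/17 = 0.033.

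**Step 2: variance of one cluster's change within type.** V = 2 x 0.25 x (1 - ICC)/18 + 2 x 0.25 x ICC x (1 - r).
- r = 0: 0.0269 + 0.0165 = 0.0433
- r = 0.5: 0.0269 + 0.0082 = 0.0351

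**Step 3: true SE of one arm-versus-control DiD under stratified allocation.** sqrt(2V/42) = 0.0454 (r = 0) and 0.0409 (r = 0.5).

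**Step 4: clustered SE reported without facility type x POST.** The between-type variance of change is B = sum(p d^2) - (sum(p d))^2, and the reported SE is sqrt(2(V + B)/42). For shares 60/30/10 and changes 0/10/20 points, B = 0.0070 - 0.0025 = 0.0045. At r = 0.5 the reported SE is sqrt(2 x 0.0396/42) = 0.0434, which is 6.2% above 0.0409.

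**Step 5: power for a 10-point effect.** With the term: Phi((0.10 - 1.96 x true SE)/true SE). Without it: Phi((0.10 - 1.96 x reported SE)/true SE). Losses are taken before rounding.

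| r | Shares | Change by type (points) | True SE | Reported SE | Too wide by | Power with | Power without | Loss (points) |
|---|---|---|---|---|---|---|---|---|
| 0 | 80/15/5 | 0/5/10 | 0.0454 | 0.0458 | 0.8% | 59.5% | 58.9% | 0.6 |
| 0 | 60/30/10 | 0/5/10 | 0.0454 | 0.0460 | 1.3% | 59.5% | 58.6% | 1.0 |
| 0 | 80/15/5 | 0/10/20 | 0.0454 | 0.0469 | 3.3% | 59.5% | 57.0% | 2.5 |
| 0 | 60/30/10 | 0/10/20 | 0.0454 | 0.0477 | 5.1% | 59.5% | 55.6% | 3.9 |
| 0.5 | 80/15/5 | 0/5/10 | 0.0409 | 0.0413 | 1.0% | 68.7% | 67.9% | 0.7 |
| 0.5 | 60/30/10 | 0/5/10 | 0.0409 | 0.0415 | 1.6% | 68.7% | 67.5% | 1.1 |
| 0.5 | 80/15/5 | 0/10/20 | 0.0409 | 0.0425 | 4.0% | 68.7% | 65.8% | 2.8 |
| 0.5 | 60/30/10 | 0/10/20 | 0.0409 | 0.0434 | 6.2% | 68.7% | 64.2% | 4.4 |

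With no difference in change, B = 0 and the two columns agree. For 0/10/20, the true type I error of the nominal 5% test is 3.7-4.3%. Taking r up to 1 raises the largest losses only to 1.2 points (0/5/10) and 4.7 points (0/10/20).

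**Step 6: equation (1) read literally, with independent errors.** SE = sqrt(4 x 0.25/756) = 0.0364. Against the true SE this is 20% too narrow at r = 0 (type I error about 12%), 11% at r = 0.5 (about 8%) and 4% at r = 0.8 (about 6%). It is 2% too wide only at r = 1.

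**Step 7: main effect alone.** In simulation (1,500 runs per scenario), adding facility type without its interaction with POST left the mean clustered SE at 0.0454.

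**The case against.** The strongest objection is about direction. A reader might infer that the planned analysis gives error bars that are too wide and a conservative test. The documents do not support that. They specify neither clustered nor facility-level SEs, and step 6 shows that the equation as written usually gives SEs that are too narrow. Adding the stratum terms alone would not cure this. In a simulation with independent errors (2,500 runs, r = 0.5, shares 70/20/10, changes 0/10/20), it moved the SE only from 0.0363 to 0.0361 and left type I error at 8-9%. This objection stands, so the point is conditional on clustering.

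The second objection is about size. A change that differs by 20 points between facility types is twice the effect the trial is designed to detect, and no document suggests it. For milder differences the loss is about 1 power point. This also stands, and it limits the weight of the point.

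A reader might also expect a larger loss for facility-level outcomes such as absenteeism or mystery-client scores, because facility type probably predicts their level. Level is not the issue: facilities are visited at both waves, so a constant type effect cancels. The documents give nothing from which to size differential change in these outcomes.

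None of this removes the mismatch between how facilities are allocated and how the data are analysed.

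**Conclusion.** The point holds in a limited, conditional form. Facility type defines the strata, is absent from the model, and is unlikely to enter through the covariate rule. Given facility-clustered SEs, leaving out facility type x POST gives up some precision when change differs by type: about 1 power point for 0/5/10 and about 2.5-4.5 points for 0/10/20 (for example 64% against 69%). The estimate is unbiased and the analysis is valid without the term. These sizes use the plan's 42 clusters, 18 women, 50% prevalence and design effect. They also rest on shares, a between-wave correlation, an alpha and differences in change that the documents do not give. This is a free improvement and does not threaten the trial. It is still worth making, because DiD power for 10 points is only about 60-69% at correlations of 0 to 0.5.

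**What to change.** Add facility type (three levels) and facility type x POST to equation (1) and to every Aim 2 DiD model. Name them as design variables kept whatever their significance or balance. State in the same sentence that SEs are clustered by facility, since the added terms do not deliver their benefit without that. A facility-type main effect alone does not help the DiD contrast.

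The cost is four degrees of freedom (two for type, two for its interaction with POST) and a sentence or two in the analysis plan. No new data are needed: facility type must already be known for all 147 facilities in order to stratify.
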